Table 2 Summary of Design of Clinical Studies Performed to Date with QVLP	27
Table 3 Study Administrative Structure	33
Table 4 Study Treatment Groups	33
Table 5 Estimated Blood Volume Drawn	43
Table 6 Severity Grades for Solicited Local and Systemic AEs	53
Table 7 Clinical Laboratory Tests.	54

SYNOPSIS

Sponsor:	Medicago USA Inc.	
Investigational Product:	Adjuvanted Recombinant Quadrivalent VLP Influenza Vaccine (QVLP)	
Active Substance(s):	Mix of recombinant H1, H3, and two B hemagglutinin proteins expressed as virus-like particles (VLP) for the 2020-2021 Northern Hemisphere influenza virus strains	
Adjuvant	AS03 (produced by GlaxoSmithKline)	
Control Products:	Active comparators: Fluzone® High-Dose Quadrivalent (produced by Sanofi Pasteur); 2020-2021 Northern Hemisphere influenza virus strains¹ (Fluzone HD Quad) QVLP (unadjuvanted) for the 2020-2021 Northern Hemisphere influenza virus strains	
Protocol Title:	A Randomized, Partially-Blinded, Active Comparator-Controlled, Dose-Ranging, Safety, Tolerability, and Immunogenicity Phase 1/2 Study of an Adjuvanted Seasonal Recombinant Quadrivalent VLP Influenza Vaccine in Adults 65 Years of Age and Older	
Protocol Number:	CP-PRO-AdjQVLP-020	
Development Phase:	Phase 1/2	
Study Center(s):	The study will be conducted at multiple sites.	
Study Rationale:	This Phase 1/2 study is to assess the safety, tolerability, and immunogenicity of adjuvanted recombinant QVLP in healthy adults 65 years of age and older. One dose of the following vaccine formulations will be administered in this study:	
	 30 μg/strain of QVLP adjuvanted with AS03, or 30 μg/strain of QVLP unadjuvanted, or Fluzone HD Quad. 	

¹ Fluzone® High-Dose Quadrivalent is licensed in the US and expected to be commercially available for the 2020-2021 influenza season.

Planned Study Period:	The total planned study period is approximately 17 months. Subject enrollment will continue for approximately 4 to 5 months. Biological samples for immunogenicity assessments will be collected over 4 weeks post-vaccination, and long-term safety follow up and evaluation of durability of the immune responses will continue 6 and 12 months after administration of the vaccines.
Study Objectives Primary Objectives:	The primary objectives of the study are: Safety: To assess the safety and tolerability of a single dose of QVLP (30 µg/strain) with AS03 adjuvant compared to QVLP (30 µg/strain) (unadjuvanted) and Fluzone HD Quad; Immunogenicity:
	• To assess the immunogenicity of a single dose of QVLP (30 µg/strain) with AS03 adjuvant compared to QVLP (30 µg/strain) (unadjuvanted) and Fluzone HD Quad, as measured by hemagglutination inhibition (HI) assay against homologous influenza strains.
Secondary Objectives:	The secondary objectives of this study are: Immunogenicity: • To assess the immunogenicity of a single dose of QVLP (30 μg/strain) with AS03 adjuvant compared to QVLP (30 μg/strain) (unadjuvanted) and Fluzone HD Quad, as measured by microneutralization (MN) assay against homologous influenza strains; • To assess the immunogenicity of a single dose of QVLP (30 μg/strain) with AS03 adjuvant compared to QVLP (30 μg/strain) (unadjuvanted) and Fluzone HD Quad, as measured by HI assay against heterologous influenza strains; • To assess the immunogenicity of a single dose of QVLP (30 μg/strain) with AS03 adjuvant compared to QVLP (30 μg/strain) (unadjuvanted) and Fluzone HD Quad, as measured by HI (homologous and heterologous influenza strains) and MN (homologous influenza strains) assays, stratified by prior influenza vaccination status, if >25% of the enrolled subjects have received a standard influenza vaccine during the 12 months prior to study vaccination; • To evaluate the persistence of antibody responses, as determined by HI titers against homologous influenza strains, at 6 and 12 months post-vaccination;
	_

	(30 μg/strain) (unadjuvanted) and Fluzone HD Quad, stratified by prior influenza vaccination status, if >25% of the enrolled subjects have received a standard influenza vaccine during the 12 months prior to study vaccination.	
Number of Planned Subjects:	Approximately 120 healthy adult subjects 65 years of age and older are planned for randomization in a 1:1:1 ratio to receive QVLP at a dose of 30 µg/strain with AS03 adjuvant or QVLP (30 µg/strain) (unadjuvanted) or Fluzone HD Quad.	
Sample Size Determination:	The sample size up to approximately 120 subjects with 40 subjects in each treatment group will make it possible to perform the initial evaluation of vaccine immunogenicity and detect gross differences in rates of adverse events. The sample size is not large enough to detect all types of adverse reactions, including less frequent or rare events. The objective of this study is to quantify the type, percentage, duration, intensity, and relationship of common post-vaccination safety events to determine if they differ clinically among the treatment groups.	
Study Population:	Healthy male and female subjects 65 years of age and older will be included in the study.	
Dosage and Administration:	On Day 0, subjects will receive one intramuscular (IM) injection into the deltoid region of the non-dominant (if possible) arm, of their assigned treatment: • 30 µg/strain of QVLP adjuvanted with AS03, or • 30 µg/strain of QVLP unadjuvanted, or • Fluzone HD Quad. The volume of injection will be 0.7 mL for all treatments.	
Study Design:	This is a randomized, partially-blinded, active comparator-controlled, multicenter, Phase 1/2 dose-finding, safety, tolerability and immunogenicity study. The influenza strain composition of the vaccines used in this study will be based on the recommended World Health Organization (WHO) strains for vaccination in the 2020-2021 season in the Northern Hemisphere. Approximately 120 healthy male and female subjects 65 years of age and older will be enrolled into three treatment groups: QVLP given at a dose level of 30 µg/strain with AS03 adjuvant	
	Approximately 120 healthy male and female subjects 65 year of age and older will be enrolled into three treatment groups:	

Treatment Group	Treatments	Dose Level	No. of Subjects
1	QVLP adjuvanted with AS03	30 μg/strain	40
2	QVLP unadjuvanted	30 μg/strain	40
3	Fluzone HD Quad	60 μg/strain	40

The first 3 subjects per treatment group enrolled in the study will receive an IM injection of one of the three treatments listed in the table above. The vaccinations for the first three subjects in each treatment group will be staggered so that each vaccination must be performed at least 30 minutes apart. The seven-day safety data will be collected from these subjects and reviewed by the Independent Data Monitoring Committee (IDMC), prior to permitting the vaccination of the remaining subjects in these three treatment groups.

Subjects will be screened up to seven days in advance of the vaccine administration and will demonstrate a satisfactory baseline medical assessment by medical history, general physical examination, urinalysis, haematological and blood biochemistry analyses, and serum screening for HIV, Hepatitis B and Hepatitis C markers. On Day 0, vaccine administration will occur. Phone contacts will be made one day and eight days after the vaccine administration, specifically for review of the subject's safety and concomitant medication data. Visits to the Investigator site will occur 3 days after the vaccine administration (Day 3) for key safety assessments and 28 days after the vaccine administration (Day 28) for key safety and immunogenicity assessments. Subjects will have monthly telephone calls after Day 28 up to the end of the study. Subjects will return to the Investigator site on Day 182 for immunogenicity and safety assessments (6-month follow-up) and on Day 365 for final immunogenicity and safety assessments (12-month follow-up).

Subjects enrolled and vaccinated in the QVLP (15 μ g/strain and 45 μ g/strain) adjuvanted with AS03 adjuvant (full dose or half dose) and the QVLP (30 μ g/strain) adjuvanted with AS03 adjuvant (half dose) treatment groups will complete study procedures as outlined above and will be followed for safety and immunogenicity assessments up to Day 365.

Blinding

In this study, a partially-blinded design is applied whereby the following individuals will not have access to treatment allocation (i.e. remain "blind") throughout the entire study duration: the subjects, the Investigators and all personnel involved in the clinical conduct of the study (except the staff

involved in the preparation and administration of the study vaccine, the quality assurance auditor, and quality control reviewers), Medicago clinical staff and medical staff involved in safety evaluations (e.g. causality assessments), and all personnel involved in sample analysis at the central and testing (HI and MN) laboratories.
The IDMC and the independent statistician involved in the preparation of the safety data summary for the IDMC reviews will have access to or be aware of treatment allocation (i.e. be "unblinded"). The IDMC will review safety data and will make recommendations for the entire duration of the study.
In addition, select personnel of the third-party statistical team will have access to treatment allocation (i.e. be "unblinded") for the entire duration of the study since these personnel will be involved in the Day 28 data analysis and the Day 182 data analysis (see Statistical Methods section below).
A small number of Medicago personnel will have access to the Day 28 and Day 182 data analyses (i.e. be "unblinded" to results and/or treatment allocation) and will be able to look at data throughout the study. The Medicago personnel will include senior personnel in Scientific and Medical Affairs, Biostatistics, Safety, Product Development, and Regulatory Affairs.
Clinical safety assessments will include repeated urine, blood chemistry and haematology testing. Safety and tolerability endpoints will include immediate adverse events (AEs) (30 minutes post-vaccination), solicited local and systemic AEs (up to seven days post-vaccination), unsolicited AEs up to Day 28, serious AEs (SAEs), AEs leading to withdrawal, AEs of special interest (AESIs), medically attended AEs (MAAEs), new onset of chronic diseases (NOCDs), and deaths up to the end of the study (Day 365).
Vaccine immunogenicity will be evaluated on Day 0, Day 28, Day 182, and Day 365, as measured by the serum HI and on Day 0 and Day 28 as measured by MN antibody titers.
Safety:
The primary safety endpoints are:
 Occurrences, intensity, and relationship to vaccination of immediate AEs (30 minutes post-vaccination);

- Occurrences and intensity of solicited local and systemic AEs (for seven days following study vaccine administration);
- Occurrences, intensity, and relationship of unsolicited AEs for 28 days following study vaccine administration;
- Number and percentage of subjects with normal and abnormal, clinically significant urine, haematological and blood biochemistry values, and urinalysis at Days 0, 3, and 28;
- Occurrences of SAEs, AEs leading to withdrawal, AESIs, MAAEs, NOCDs, and deaths up to Day 28;
- Occurrences of SAEs, AEs leading to withdrawal, AESIs, MAAEs, NOCDs, and deaths from Day 29 up to Day 182;
- Occurrences of SAEs, AEs leading to withdrawal, AESIs, MAAEs, NOCDs, and deaths from Day 183 up to the end of the study (Day 365).

Immunogenicity:

The primary immunogenicity endpoint is:

• HI antibody response induced by adjuvanted and unadjuvanted QVLP and Fluzone HD Quad against the homologous influenza strains on Day 28, compared to Day 0 values. HI antibody titers will be analyzed using the following parameters: geometric mean titers (GMT), seroconversion (SC) rate, seroprotection (SP) rate, and geometric mean fold rise (GMFR).

Secondary Endpoints:

Immunogenicity:

The secondary immunogenicity endpoints are:

- MN antibody response induced by adjuvanted and unadjuvanted QVLP and Fluzone HD Quad against the homologous influenza strains on Day 28, compared to Day 0 values. MN antibody titers will be analyzed using the following parameters: GMT, SC rate, and GMFR;
- HI antibody response induced by adjuvanted and unadjuvanted QVLP and Fluzone HD Quad against the heterologous influenza strains on Day 28, compared to Day 0 values. HI antibody titers will be analyzed using the following parameters: GMT, SC rate, SP rate, and GMFR.
- HI antibody response (against homologous and heterologous influenza strains) and MN antibody response (against homologous influenza strains) induced by adjuvanted and unadjuvanted QVLP and Fluzone HD

- Quad on Day 28, compared to Day 0 values, stratified by prior influenza vaccination status, if >25% of the enrolled subjects have received a standard influenza vaccine during the 12 months prior to study vaccination;
- Durability of antibody responses, as determined by HI titers against homologous influenza strains (6 and 12 months post-vaccination);

Safety:

The secondary safety endpoints are:

- Occurrences, intensity, and relationship to vaccination of immediate AEs (30 minutes post-vaccination), stratified by prior influenza vaccination status, if >25% of the enrolled subjects have received a standard influenza vaccine during the 12 months prior to study vaccination;
- Occurrences and intensity of solicited local and systemic AEs (for seven days following study vaccine administration), stratified by prior influenza vaccination status, if >25% of the enrolled subjects have received a standard influenza vaccine during the 12 months prior to study vaccination;
- Occurrences, intensity, and relationship of unsolicited AEs for 28 days following study vaccine administration, stratified by prior influenza vaccination status, if >25% of the enrolled subjects have received a standard influenza vaccine during the 12 months prior to study vaccination;
- Number and percentage of subjects with normal and abnormal, clinically significant urine, haematological and blood biochemistry values, and urinalysis at Days 0, 3, and 28, stratified by prior influenza vaccination status, if >25% of the enrolled subjects have received a standard influenza vaccine during the 12 months prior to study vaccination;
- Occurrences of SAEs, AEs leading to withdrawal, AESIs, MAAEs, NOCDs, and deaths up to Day 28, stratified by prior influenza vaccination status, if >25% of the enrolled subjects have received a standard influenza vaccine during the 12 months prior to study vaccination;
- Occurrences of SAEs, AEs leading to withdrawal, AESIs, MAAEs, NOCDs, and deaths from Day 29 up to Day 182, stratified by prior influenza vaccination status, if >25% of the enrolled subjects have received a standard influenza vaccine during the 12 months prior to study vaccination;

• Occurrences of SAEs, AEs leading to withdrawal, AESIs, MAAEs, NOCDs, and deaths from Day 183 up to the end of the study (Day 365), stratified by prior influenza vaccination status, if >25% of the enrolled subjects have received a standard influenza vaccine during the 12 months prior to study vaccination.

Statistical Methods:

Populations:

Statistical analyses will be performed on pre-defined population sets (the safety analysis set [SAS], the intention-to-treat [ITT] set, and the per protocol [PP] set) according to the Statistical Analysis Plan (SAP).

All safety analyses will be performed using the SAS. The analyses of all immunogenicity endpoints will be performed using the PP set and the ITT set. The analysis in the PP set will be considered the primary analysis for these objectives in order to collect information regarding the immunogenicity responses that most closely reflect the scientific model underlying the protocol. ITT set will be used as sensitivity analysis.

Day 28 and Day 182 Data Analyses:

The third-party statistical team will perform data analyses after Day 28 (last subject) and Day 182 (last subject). The data analyses will involve select individuals from the third-party statistical team and Medicago who will be unblinded (as described in Blinding section above). The Day 28 and Day 182 data analyses will allow discussions of the clinical data to inform study design decisions of the subsequent study, without having to wait until after the end of the follow-up period for study completion.

Statistical Analyses:

All descriptive and inferential statistical analyses will be performed using Statistical Analysis System[®] (SAS[®]) software (version 9.4 or higher).

In general, categorical data will be summarized using the number and percent of subjects in each category and continuous data will be summarized using descriptive statistics (mean or geometric mean, median, standard deviation, minimum, and maximum).

Analyses of the immunogenicity and safety endpoints will include each group as a whole as well as comparisons by prior influenza vaccination status, if >25% of the enrolled subjects

have received a standard influenza vaccine during the 12 months prior to study vaccination.

Safety Analyses:

Safety and tolerability endpoints will be summarized by treatment using descriptive statistics.

Immunogenicity Analyses:

For both HI and MN, point estimates and two-sided 95 % CI for all immunogenicity endpoints and responses for the treatment groups will be calculated. GMT will be compared among treatment groups by using Analysis of Variance (ANOVA) on log-transformed data. GMFR will be derived by using Analysis of Covariance (ANCOVA) to model the difference in the log of the titer values between Day 28/182/365 and Day 0 for the HI assay and between Day 28 and Day 0 for the MN assay, with treatment group as main effect and baseline titer as covariate. For GMT and GMFR comparisons, Tukey's test will be performed to show p-values for the pairwise comparisons between treatment groups. Fisher's exact tests or chi square tests will be used to compare SC among treatment groups.

Table 1 Time and Events Schedule: General Information

Visit Type	Screening	Vaccination	Post-vaccination Visits/Contacts						
Study Day	Day -7 to 0	Day 0	Day 1 (+ 1)	Day 3 (± 1)	Day 8 (+ 1)	Day 28 (± 2)	Monthly Calls ⁸ (± 14)	Day 182 (± 14) 10	Day 365 (± 14)
Visit Number	1	2	Phone	3	Phone	4	Phone	5	6
Informed consent	X								
Demographics	X								
Medical history/prior medication ⁷	X	X ¹							
Inclusion/exclusion criteria ⁷	X	X							
Physical examination ²	X	X		X					
Vital Signs ⁷	X	X^3		X		X		X	X
Height, weight, and BMI ⁷	X	X							
Urinalysis	X			X		X			
Blood chemistry and Hematology	X ⁹			X		X			
Serum for HIV, Hepatitis B, and Hepatitis C	X								
Serum sample for HI and MN		X				X		X ¹¹	X ¹¹
Randomization		X							
Vaccine administration		X							
Immediate surveillance (30 minutes)		X							
Provide diary and memory aid instructions (manual or electronic)		X							
Oral digital thermometer and instructions on AEs ⁴		X							
Collection of solicited local/systemic AEs		X	X	X	Х				
Concomitant medications ⁵		At any time during the study period							
AEs, SAEs, AESI, MAAEs, and NOCDs ⁶		At any time during the study period							
Termination record									X

¹ Record any changes in medical history and medications and confirmation that the subject continues to meet all inclusion and no exclusion criteria since screening.

² A limited physical examination will occur at screening, Day 0, and Day 3. History/symptom-directed physical examinations may be at Day 28, Day 182, and Day 365 visits if 1) new complaints or concerns are raised by either the study subject or study staff and 2) deemed to be necessary by the Investigator.

³ Record prior to study vaccine, after the observation period and as deemed necessary.

⁴ After vaccination, subjects will be instructed on the diary and memory aid (manual or electronic) provided for their use for recording AEs and concomitant medication use.

⁵ After the Day 28 visit, concomitant medication collection will be limited to those used to treat a NOCD, SAE, AE leading to withdrawal, AESIs, MAAEs, or an AE that occurred before Day 28; any vaccine not foreseen in the study protocol; and prohibited medications.

⁶ AEs will be collected up to Day 28; SAEs, AEs leading to withdrawal, AESIs, MAAEs, and NOCDs will be collected through to the end of the study. Specific contacts for the collection of information regarding all these events will occur on Day 365 (during the Day 365 final visit) for SAEs, AEs leading to withdrawal, AESIs, MAAEs, and NOCDs.

⁷ If screening and vaccination occur on the same day (Day 0), then this test and/or procedure should only be performed once prior to randomization.

Visit Type	Screening	Vaccination	Post-vaccination Visits/Contacts						
Study Day	Day -7 to 0	Day 0	Day 1 (+ 1)	Day 3 (± 1)	Day 8 (+ 1)	Day 28 (± 2)	Monthly Calls ⁸	Day 182 (± 14) 10	Day 365
Visit Number	1	2	Phone	3	Phone	4	Phone	5	6

⁸ Subjects should be reached once a month with no more than 45 days between phone contacts (use Day 28 date as starting reference).

⁹ Sample blood collection at screening should be performed under fasting conditions (approximately 12 hours) for cholesterol and triglyceride analyses. Cholesterol and triglyceride analysis will only be performed at screening.

¹⁰ For some subjects, the Day 182 visit may occur during the time the subject may want to receive the 2021-2022 seasonal influenza vaccine. Hence, the tests/procedures (including immunogenicity sample collection) originally planned for the Day 182 visit will be collected at the Day 182 timepoint or immediately prior to administration of the 2021-2022 seasonal influenza vaccine (whichever comes first).

¹¹ Only HI assay will be performed on the serum sample collected at Day 182 and Day 365.

ABBREVIATIONS

ACIP Advisory Committee on Immunization Practices

AE adverse event

ANOVA analysis of variance
BMI body mass index
BP blood pressure

CBER Center for Biologics Evaluation and Research

CI confidence interval

CMI cell-mediated immune (response)
eCRF electronic case report form
FDA Food and Drug Administration

GCP good clinical practice

GMFR geometric mean fold rise or seroconversion factor

GMT geometric mean titer

HI hemagglutination inhibition

HR heart rate

IB investigator's brochure ICF informed consent form

ICH International Council for Harmonisation

IEC independent ethics committee

IM intramuscular

IRB institutional review board

ITT intention-to-treat

MAAE medically attended adverse event

MedDRA Medical Dictionary for Regulatory Activities

MN microneutralization

NACI National Advisory Committee on Immunization

NOCD new onset of chronic disease

OT oral temperature PP per protocol

SAE serious adverse event
SAP statistical analysis plan
SAS safety analysis set

SAS[®] Statistical Analysis System[®]

SC seroconversion SP seroprotection

SRH single radial hemolysis

TEAE treatment-emergent adverse event

VLP virus-like particle

WHO World Health Organization

US United States

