10.3.2.1 Primary Endpoint

- HI antibody response induced by adjuvanted and unadjuvanted QVLP and Fluzone HD Quad against the homologous influenza strains on Day 28, compared to Day 0 values, will be analyzed as follows:
 - GMTs of HI antibody on Days 0 and 28;
 - SC rate: the proportion of subjects in a given treatment group with either a ≥ 4-fold increase in reciprocal HI titers between Day 0 and Day 28 or a rise of undetectable HI titer (i.e. < 10) pre-vaccination (Day 0) to an HI titer of ≥ 40 on Day 28;
 - SP rate: the proportion of subjects in a given treatment group attaining a reciprocal HI titer of ≥ 40 on Day 28 (the percentage of vaccine recipients with a serum HI titer of at least 1:40 following vaccination);
 - GMFR: the geometric mean of the ratio of GMTs (Day 28/Day 0).

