12.6 Immunogenicity Analyses

12.6.1 Analysis of Primary Endpoint

The primary immunogenicity endpoint is defined in Section 10.3.2.1.

The following analyses for the HI assay (homologous strains) will be performed on the PP set:

- GMT (Day 0 and Day 28): The point estimates and the corresponding two-sided 95 % CI by treatment group and strain will be calculated as the antilog of the mean and 95 % CI of log transformed titer values;
- SC rate (Day 28): The point estimates and the corresponding two-sided 95 % CI for subjects achieving SC by treatment group and strain will be calculated and reported;
- SP rate (Day 0 and Day 28): The point estimates and the corresponding two-sided 95 % CI for subjects achieving SP by treatment group and strain will be calculated and reported;
- GMFR: the geometric mean of the ratio of GMTs (Day 28/Day 0).

The GMFR will be derived by using ANCOVA to model the difference in the log of the titer values between Day 28 and Day 0, with treatment group as main effect and baseline titer as covariate.

GMT for HI will be compared between treatment groups using the analysis of variance (ANOVA) model. GMFR for HI will be compared using the ANCOVA model. For SC rate and SP rate, Fisher's exact tests or chi square tests will be used to compare between the treatment groups.

Analyses of primary immunogenicity endpoint will include each group as a whole.

The analyses of the primary immunogenicity endpoints will also be performed using the ITT set.

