# 8.1. Primary Immunogenicity Analysis

The primary immunogenicity analysis endpoint is to evaluate the HI antibody response induced by adjuvanted and unadjuvanted QVLP and Fluzone HD Quad against the homologous influenza strains on Day 28, compared to Day 0 values, analyzed as follows:

- GMT at Day 0 and Day 28;
- SC rate at Day 28: the proportion of subjects in a given treatment group with either a ≥ 4-fold increase in reciprocal HI titers between Day 0 and Day 28 or a rise of undetectable HI titer (i.e., < 10) pre-vaccination (Day 0) to an HI titer of ≥ 40 on Day 28:
- SP rate at Day 28: the proportion of subjects in a given treatment group attaining a reciprocal HI titer of ≥ 40 on Day 28 (the percentage of vaccine recipients with a serum HI titer of at least 1:40 following vaccination);
- GMFR (Day 28/Day 0): the geometric mean of the ratio of GMTs (Day 28/Day 0).

For the H1 and H3 analysis, results from the assay using VLP reagents will be used. Any antibody titer that is below the LLOQ of assay will be imputed with a value equal to half of the LLOQ of assay of the antigen specific antibody titer.

GMT will be calculated as anti-logarithm of ( $\sum$ (log-transformed titer)/number of subjects with titer information). The 95% CI for GMT will be calculated as the anti-log transformation of upper and lower limits for a 2-sided CI of the mean of the log-transformed titers. The log-transformed GMT will be compared among treatment groups by using the analysis of variance (ANOVA) model on log-transformed titer values and the Tukey's test will also be performed for the pairwise comparisons between treatment groups within the frame of the same model.

The point estimates and the corresponding two-sided 95 % Clopper-Pearson CI [Clopper, 1934] for subjects achieving SC and SP will be calculated and compared among treatment groups using Fisher's exact test.

GMFR will be calculated as anti-logarithm of  $\sum$  [log-transformed titer ratio of Yi/Bi)/number of subjects with titer information], where Yi is the post-vaccination titer and Bi is the pre-vaccination (baseline) titer for subject i. The 95% CI for GMFR will be calculated as the anti-log transformation of upper and lower limits for a 2-sided CI of the mean of the log-transformed titers fold rise from pre-vaccination. The log-transformed

Medicago USA Page **32** of **55** 

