#### Analysis of SC/SP

• 95% CI

PROC FREQ data=tab;

BY STRAIN TRT;

TABLE var / binomial (exact); \*\* where var=Subject achieving SC or SP

RUN:

• Fisher's Exact Test:

PROC FREQ data=tab;

BY STRAIN;

TABLE var\*TRT/ fisher; \*\* where var=Subject achieving SC or SP

RUN:

Note: The MN assay will be performed on Day 0 and Day 28 only, and not on Day 182 and Day 365.

Confidential

Medicago USA Page 48 of 55

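### The Day 28 seroprotection comparison makes no use of the Day 0 titer: the test is valid but less precise than the data allow

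*Protocol*

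**What the plan says.** The Protocol synopsis describes the primary HI endpoint as the response "against the homologous influenza strains on Day 28, compared to Day 0 values", analysed through GMT, seroconversion (SC), SP and GMFR. Protocol 10.3.2.1 defines SP as "the proportion of subjects in a given treatment group attaining a reciprocal HI titer of ≥ 40 on Day 28", so Day 0 plays no part in it.

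For the comparison, Protocol 12.6.1 says "For SC rate and SP rate, Fisher's exact tests or chi square tests will be used to compare between the treatment groups". SAP 8.1 narrows this: exact confidence intervals "for subjects achieving SC and SP will be calculated and compared among treatment groups using Fisher's exact test". The code in SAP 13.3 is "TABLE var\*TRT/ fisher", run by strain, with no covariate or baseline stratum. The synopsis names these tests for SC only.

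Day 0 enters elsewhere. SC is defined by change from Day 0. GMFR is compared by ANCOVA with log baseline titer as covariate (SAP 8.1 and 13.3). Protocol 12.6.1 also reports "SP rate (Day 0 and Day 28): The point estimates and the corresponding two-sided 95 % CI" by arm, whereas SAP 8.1 lists SP at Day 28 only. The Day 28 per-protocol set requires both a Day 0 and a Day 28 sample (Protocol 12.1.3; SAP 4.4.4).

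**The concern.** No eligibility criterion limits the Day 0 HI titer. Influenza vaccine is excluded only within the previous six months, and the plan allows for more than 25% of subjects having been vaccinated within twelve. Some subjects may therefore already be at 40 or above before the injection. With 40 per arm, that share will differ between arms by chance, and the planned table test has no means of accounting for it. The sponsor treats Day 0 titer as prognostic for fold rise but leaves it out of the SP comparison.

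At stake is the precision of one of four primary immunogenicity parameters, for each of four strains, in a study whose HI results inform the formulation and design of later trials (Protocol 12.3; SAP 10).

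**Working it through.** **Inputs from the documents.** 40 subjects per arm (Protocol 12.2; SAP 4.1). SAP 4.1 states that no sample size calculation was done, so there is no SP power or effect size to reproduce.

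**Assumed inputs.** The documents give no Day 0 SP rate, titer SD or Day 0/Day 28 correlation. Let q be the share at 40 or above on Day 0, taken as 0.2 to 0.8. For the precision check, two arms of 40 were simulated:
- log2 Day 0 titer is normal with mean 4.8 and SD 1.7, which puts about 38% at 40 or above.
- Day 28 log2 titer = 4.8 + 1.1 + slope × (Day 0 − 4.8) + effect + residual, with effect 0 or 1 (a two-fold titer effect).
- Slope / residual SD are 0.40/1.5, 0.55/1.3 and 0.75/1.0, giving correlations of 0.41, 0.58 and 0.79.
- Expected SP is about 64% against 83%.

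**Step 1. Chance imbalance in Day 0 SP between two arms.** SD = √(2q(1−q)/40).
- q = 0.2 or 0.8: √(0.32/40) = 8.9 points.
- q = 0.5: √(0.50/40) = 11.2 points.
- q = 0.38: √(0.4712/40) = 10.9 points, a 95% range of ±1.96 × 10.9 = ±21 points.

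This ignores stratified allocation, which would reduce it somewhat.

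**Step 2. How much carries over.** A point of Day 0 imbalance moves the SP difference by P(Day 28 ≥ 40 given Day 0 ≥ 40) − P(Day 28 ≥ 40 given Day 0 < 40). In the simulated model this is about 0.2 at the lowest correlation and about 0.5 at the highest. An imbalance at the edge of the ±21-point range therefore shifts the SP difference by about 21 × 0.2 = 4 to 21 × 0.5 = 11 points.

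**Step 3. Precision and power.** The adjusted analysis is Firth logistic regression on treatment and log Day 0 titer. Mantel-Haenszel (MH) is stratified by Day 0 titer < 40 / ≥ 40.

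| Assumed correlation | 0.4 | 0.6 | 0.8 |
|---|---|---|---|
| Fall in SD of SP difference, log-titer covariate (r) | 6% | 12% | 22% |
| Equivalent extra subjects, 1/(1−r)² − 1 | 13% | 29% | 64% |
| Fall in SD, MH | 2–3% | 4–6% | 9–12% |
| Power, Fisher | 43% | 42% | 46% |
| Power, adjusted | 54% | 57% | 71% |
| Power gain from leaving Fisher (points) | about 9 | about 9 | about 9 |
| Power gain from baseline (points) | about 2 | about 6 | about 17 |

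**Step 4. Type I error.** With no effect, Fisher rejects in about 3% of simulated trials and the adjusted test in 4.3–5.4%. Fisher is conservative, not anti-conservative.

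**Step 5. Dilution is a separate matter.** If everyone at 40 or above on Day 0 stays there, the SP difference is (1−q)(p1−p2), where p1 and p2 are the rates among subjects below 40. With 80% against 50%, the 30-point effect becomes 24, 18, 12 and 6 points at q = 0.2, 0.4, 0.6 and 0.8. Adjustment does not undo this: in the Step 3 model the mean SP difference is about 19–20 points with or without it.

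**The case against.** The strongest reply is that a randomized Fisher comparison needs no baseline term. Chance imbalance is already part of its null distribution. This stands. A reader might infer that the SP result is confounded, or that Day 0 imbalance passes one for one into it; neither follows, since type I error is about 3% and the carry-over is partial.

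A second reply is that the plan covers baseline elsewhere. GMFR is baseline-adjusted, SC uses Day 0, the Protocol reports Day 0 SP by arm, reverse cumulative distribution curves are planned, and HI analyses are repeated by prior vaccination status if more than 25% were vaccinated. Randomization is also stratified by that status, though the SAP says only from protocol version 3.0. These help the reader of the whole endpoint, but none makes the SP comparison itself more precise.

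Third, the phrase "against the homologous influenza strains on Day 28, compared to Day 0 values" describes the HI endpoint as a whole and does not require a baseline-conditioned SP test. That is right; the case for change is efficiency, not breach of the endpoint definition.

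Fourth, the study has no SP success criterion or confirmatory hypothesis, and all titer inputs here are assumed. Both are true and limit the weight of the point. The simulation also compares two arms, whereas the planned table spans the treatment groups, and SAP 4 includes the stopped groups in the analyses.

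**Conclusion.** The point holds as a loss of precision in one of four primary immunogenicity parameters, not as an error of validity. The planned SP comparison leaves out a prognostic value that every per-protocol subject has and that the plan already uses for GMFR. The benefit of using it ranges from small (SD down about 6%) to material (about 22%), according to how strongly Day 0 and Day 28 titers correlate. The full gap between the Fisher and adjusted powers should not be credited to baseline, since about 9 points of it come from Fisher's conservatism.

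Two further inferences are not supported. Adjustment does not remove dilution by subjects already at 40 or above; it only sharpens the estimate. And the documents do not show how many subjects that is, so the 38% used in the simulation is an assumption.

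**What to change.** In SAP 8.1 and 13.3, and Protocol 12.6.1:
- Keep the per-arm SP rates with Clopper-Pearson intervals, and list SP at Day 0 by arm in the SAP, as Protocol 12.6.1 does.
- Compare SP for adjuvanted QVLP against unadjuvanted QVLP and against Fluzone HD Quad by Firth logistic regression on treatment and log10 Day 0 titer. Report the standardised SP difference with a 95% CI by delta method or bootstrap.
- Show SP among subjects with Day 0 titer below 40 as supportive information on dilution.

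MH stratified by Day 0 < 40 / ≥ 40 is a simpler fallback, with about half or less of the precision gain; it is not an equivalent. SAP 8.2 takes its methods from the primary analysis, so it should say whether the change also applies to heterologous SP and to Days 182 and 365.

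Cost: a SAP paragraph and some code, with no new data. The FIRTH option alone gives a conditional odds ratio, so the standardised difference needs a further step. The comparison becomes model-based, and the gain is small where the Day 0/Day 28 correlation is low or nearly all subjects reach 40 at Day 28.
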